## 4.7 Principles of operation of the device

### 4.7.1 Manual functionalities

The device visualizes echocardiography imaging data in a web browser and allows inspecting the imaging data and performing measurements by drawing annotations superimposed on the visualized data. The annotations are then used to calculate the relevant geometric and functional heart parameters.

### 4.7.2 Automatic functionalities

The device performs a series of steps that involve automated recognition of the echocardiography imaging data, recognition of echocardiographic probe position and detecting a set of anatomical (e.g. heart chamber borders, landmarks). The automated functionalities rely on the metadata obtained from the DICOM format (e.g. imaging mode) as well as predictions made by deep neural networks from the echocardiographic images (e.g. echocardiographic probe position recognition, heart chamber border, landmark detection).

To summarize, the input to the device is an echocardiography DICOM image. After the image is analyzed using automated and/or manual functionalities, a finalized report is generated, which is the output of the software.

## 4.8 Qualification of the product as a medical device

Definition of medical device according to EU MDR 2017/745

‘Medical device’ means any instrument, apparatus, appliance, software, implant, reagent, material, or other article intended by the manufacturer to be used, alone or in combination, for human beings for one or more of the following specific medical purposes:

- diagnosis, prevention, monitoring, prediction, prognosis, treatment or alleviation of disease;
- diagnosis, monitoring, treatment, alleviation of, or compensation for, an injury or disability;
- investigation, replacement or modification of the anatomy or of a physiological or pathological process or state;
- providing information by means of in vitro examination of specimens derived from the human body, including organ, blood and tissue donations;

UAB Ligence	Clinical Investigation Report	2021-04-09
		Rev: 1.0

- and which does not achieve its principal intended action by pharmacological, immunological or metabolic means, in or on the human body, but which may be assisted in its function by such means.

The following products shall also be deemed to be medical devices:

- devices for the control or support of conception;
- products specifically intended for the cleaning, disinfection or sterilization of devices as referred to in Article 1(4) (EU MDR 2017/745) and of those referred to in the first paragraph of this point.

Ligence Heart meets requirements which are described in definition of medical device which is placed in Medical Device Regulation 2017/745, based on the definition of a medical device:

medical device - software, intended by the manufacturer for use in humans for the purpose of:

- diagnosis, prevention, prediction, prognosis, treatment or alleviation of the disease.
- investigation, replacement or modification of the anatomy or of a physiological or pathological process or state.

## 4.9 Explanation of any novel features

Ligence Heart offers novel functionality that allows automatic analysis of a number of heart structure and function parameters. Therefore, the parameters that are analyzed themselves are not novel, but the automation of some of these measurements is novel (none of the manual functionalities are novel). The automatic functionalities are based on Deep Learning technologies (more details in the System detailed design and specification in the Technical File). These automatic functionalities offer the ability to automate activities that are usually performed manually during regular echocardiography image analysis.

[figure not shown]
## 4.10 Description of all configurations/variants of the product

There is a possibility, on the request of the customer, to have different functionalities of Ligence Heart turned on/off for each customer via the manufacturers control mechanisms. The product basic package will always allow to manually annotate images and receive calculations of measurements. The algorithms to automatically perform some of these manual tasks will be turned on/off depending on the customer needs and sale agreement.

## 4.11 General description of key functional elements

UAB Ligence	Clinical Investigation Report	2021-04-09
		Rev: 1.0

Functional elements scheme.

Explanation of functional elements

Key function	Description
1. Transfer of echocardiography images	Personal data is removed from echocardiography images (if needed) and the images are transferred from hospital PACS to Ligence Heart software
2. Analysis	Echocardiography images analysis step using automated or manual analysis
2.1. Automated analysis	
2.1.1. Automated view classification	Automated system determines the view mode of echocardiography image. This step is needed for further analysis of images
2.1.2. Automated prediction of annotations	Automated system predicts annotations that are used to measure heart anatomy based on the view mode of echocardiography DICOM image

UAB Ligence	Clinical Investigation Report	2021-04-09
		Rev: 1.0

2.1.3. Automated heart phase prediction	Automated system tracks cardiac cycle and identifies the frames that are crucial for the analysis of echocardiography images, e.g. end-systolic and end-diastolic
2.2. Manual analysis	
2.2.1. Login to the image viewer	Authentication/authorization to the software step needed to be able to access studies
2.2.2. Study selection	Selection of accessible study by filtering/searching step
2.2.3. View selection and adjustments	Study analysis step, physician sets the view mode of echocardiography image, performs annotations, or adjusts measurements already made by automated analysis
3. Calculation of measurements	Calculation of measurements based on the annotations on echocardiography image performed by the combination of manual and automatic functions
4. Report generation	Study analysis report, which consists of all annotations, measurements made along with automated suggested diagnosis text, is generated for review and approval of physician
5. Validation by medical professional	Medical professional validates all annotations and measurements made and adjusts the annotations if needed, updating the report respectively

UAB Ligence	Clinical Investigation Report	2021-04-09
		Rev: 1.0

## 4.12 State of the Art and Comparator/Reference Standard

### 4.12.1 State of the Art

The current state of the art of echocardiographic examination is thoroughly defined in the guidelines of American Society of Echocardiography (ASE), European Association of Cardiovascular Imaging (EACVI), European Association of Echocardiography (EAE) (15–22).

Based on the reviewed scientific literature, clinical guidelines, analyzed products on the market, the current state of the art is as follows:

A physician or a technician acquires echocardiography images using an up-to-date certified modern ultrasound machine. The acquired images are then analyzed either on the ultrasound machine or in post-processing using a workstation after the exam has been performed. The analysis is performed with different certified medical image analysis software (e.g. EchoPAC by GE or Intellispace Cardiovascular by Philips, which were chosen as comparator/reference standards). The heart view mode selection, choice of frames to analyze, and annotations are all performed manually by the physician according to the guidelines that are mentioned previously. To finalize, a report that includes all relevant findings is generated.

The analysis of echocardiography images is subjective and dependent on the physician's skill and ability to perform the mentioned manual tasks and therefore is prone to errors. The literature on reproducibility of echocardiographic measurements shows that intra and inter-observer variability is depended on the measurements in question and can be as high as 40% (mean error) for some measurements (23,24).

Furthermore, a comprehensive TTE examination on average lasts from 30 to 60 min but can take up to 2 hours in more complicated cases (25,26).

### 4.12.2 Comparator/Reference standards

The comparator/reference standards used for comparison with the investigational product Ligence Heart software are separated into two groups, which are based on the functionalities that are being compared:

1. Manual functionalities: Ligence Heart software's manual functionalities that are used to analyze echocardiographic images are equivalent to the ones offered by other state-of-the-art software on the market. The manual functionalities will be compared to the commercially available CE marked state-of-the-art medical image viewers Intellispace Cardiovascular 5.1 by PHILIPS, and EchoPAC version 112 software by GE. To elaborate, Ligence Heart software's ability to calculate various measurements based on the user's annotations will be compared to other state-of-the-art technologies.
2. Automatic functionalities: The automated measurements performed by Ligence Heart software do not yet have equivalents on the market and are considered novel features. The current state-of-the-art for echocardiographic image analysis is the standard manual procedure - the physician that performs the examination must perform the annotations of images manually by identifying various structures of the heart himself. Therefore, the performance of the physician is the reference standard against which the performance of automatic functionalities of Ligence Heart will be compared.

## 4.13 Accountability

Accurate and adequate records will be maintained for the use of the medical devices as required by applicable laws and regulations.

The sponsor is responsible, working together with the IT staff of the investigational site, for the installation of and access to the Ligence Heart software. The comparator software that will be used during the clinical investigation is already installed and managed by the IT staff at the investigational site and used with an official approval for the clinical investigation from the administrators of the investigational site. The sponsor's procedures for verification and documentation of device safety, traceability of software versions, device labeling, and device disposition will be followed. The Principal Investigator and the IT manager will be ultimately responsible for the security and integrity of research devices at the site during the study.

UAB Ligence	Clinical Investigation Report	2021-04-09
		Rev: 1.0

#### 4.14 Issuance

Device will be provided by the Sponsor to the site. There is no additional calibration or maintenance of study devices planned after the initial installation. The Sponsor may provide maintenance and monitoring of devices as necessary to maintain the integrity of study data. If any issues regarding the device arise, the investigators shall contact the Sponsor's staff (contacts and a more in-depth explanation provided during clinical investigation training).

#### 4.15 Disposition

The medical device software Ligence Heart will no longer be accessible from the investigational site for the investigation purposes after the clinical investigation has ended, in accordance with applicable laws and regulations. No personal information will be retained in the device after disposition, as all the data that will be included in the study will be pseudonymized with all personal information removed.

#### 4.16 Anticipated Risks

The device under study has undergone risk assessment, in accordance with International Standards Organization (ISO) 14971, and risks have been mitigated to levels as low as reasonably possible (ALARP).

Medical software does not have direct contact with subjects and no additional direct clinical procedures will be conducted for the clinical investigation. Therefore, no harm to the subjects' health is possible during the clinical investigation.

The personal data of the subjects will be processed and stored in the same way as other personal medical information: the researchers undertake to provide the client only with depersonalized (anonymous) information collected during the biomedical research.

Risk management for the medical software Ligence Heart is performed in accordance with ISO 14971:2012.

The following risks that have been identified as relevant for the clinical investigation:

- Cybersecurity breach (R-1);

The risks that have been identified as irrelevant for the clinical investigation, because they are associated with direct management and decision making of the patient's care during regular clinical practice, and during clinical investigation no direct decision making on the further subject clinical management will take place:

- Bug in the code (R-2)
- Software failure during the login and/or study selection process (R-3)
- Failure of the software to save the work progress (R-4)
- Errors of the functions that allow manipulation of the images (such as contrast changing, zooming, adding (annotations etc.) due to bugs (R-5)
- Automatic analysis of inadequate quality echocardiography images (R-6)
- Failure of 3rd party software components (R-6)
- The cloud server is unreachable (R-7)
- Incorrectly configured user's rights (R-8)
- Hardware does not have sufficient resources to run the software adequately (R-9)
- User runs Ligence Heart on incompatible software/operating system (R-10)
- Errors in the communication of the software with the hospital's information system (R-11)
- Erroneous performance of annotations/other aspects of echocardiography exam and approval of the final results by the user (R-12)
- Poor user interface design (R-13)
- Newly released software update is not validated correctly (R-14)

#### 4.17 Established Risk Control Measures

UAB Ligence	Clinical Investigation Report	2021-04-09
		Rev: 1.0

To control and minimize the relevant identified risks, risk control measures have been established.

Cybersecurity threat mitigation measures are implemented based on Eichelberg2020a article from literature review which proposes security measures to be used in healthcare IT infrastructure. Article references security related publications NIST Special publication 1800-24 “Securing Picture Archiving and Communication System (PACS)” and various European Union Agency for Network and Information Security (ENISA) articles. Main measures implemented are:

- Firewalls and network segmentation
- Whitelisting of application
- User authentication and access rights
- Encryption
- Audit trail/logging
- Ensuring secure configurations
- Client certificates
- Penetration testing
- Image de-Identification
- Transport Security

Moreover, healthcare facilities security mitigation measures are described for clients to implement according to Eichelberg2020 article from literature review which describes main attack vectors against hospitals. Security measures for hospitals:

- Physically secure location of workstations connected to the software
- Regular updates
- Antimalware software
- Communication filtering

A more extensive risk control measure analysis on the other previously mentioned risks (which are not directly applicable to the clinical investigation, however, relevant to the application of the software in a real clinical setting) can be found in the Risk management file.

## **4.18 Risk-to-benefit rationale of the investigation**

In the context of this clinical investigation, most of the risks that are identified to be associated with the use of Ligence Heart software are irrelevant, as no clinical decisions will be made based on diagnostic procedure that will take place during the investigation. The relevant risks, that have been previously described in sections 4.16 and 4.17 are strictly controlled as provided in the risk control measures description. Due to the design of the investigation, no harm to the subjects’ health is possible. Therefore, a conclusion can be made that the potential benefits of the future application of Ligence Heart software in real clinical practice and the benefits of the clinical investigation that is due to take place greatly outweigh the risks posed by this investigation.

# **5 Study Objectives and Endpoints**

## **5.1 Purpose of the Study**

The purpose of this study is to evaluate the safety and performance of the manual and automatic functionalities of medical device software Ligence Heart comparing them to the state-of-the-art alternatives.

## **5.2 Objectives**

### **5.2.1 Primary Objectives**

UAB Ligence	Clinical Investigation Report	2021-04-09
		Rev: 1.0

4. Manual measurement analysis: To calculate the reliability of Ligence Heart manual functions that are used to perform echocardiographic measurements comparing it with the manual measurements performed with other CE marked state-of-the-art medical image viewers.
5. Automatic measurement analysis: To compare Ligence Heart automatic measurements accuracy, variance, and error rate with human physicians in real clinical setting.
6. Time used comparison: To compare Ligence Heart automatic measurement tool execution time with the time it takes a physician to perform the measurements manually.

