### Expected performance

Expected performance of manual functionalities:

- The manual functionalities of Ligence Heart are expected to provide equally accurate and reliable tools for echocardiography evaluation compared to other state of the art CE marked medical software.

Expected performance of automated functionalities:

- Ligence Heart performs automated measurements with non-inferior accuracy compared to a cardiologist;
- Automatic functionalities perform echocardiographic measurements with lower intra-rater variability than a cardiologist;
- On average automatic functionalities perform the evaluation of echocardiographic images faster than a cardiologist.

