## 5.3 Study Endpoints

### 5.3.1 Primary Endpoints

The end points respectively to the objective number:

4. Echocardiographic measurements performed manually with Ligence Heart and comparator software. The inter-software reliability between manual measurements performed with Ligence Heart and other CE marked state-of-the-art medical image viewers will be calculated (Part 1 of the investigation);
5. Echocardiographic measurements performed automatically by Ligence Heart software and echocardiographic measurements performed manually by physicians. The accuracy of automatic functions of Ligence Heart will be compared with the accuracy of physicians performing measurements manually (Part 2 of the investigation);
6. Time used to perform echocardiographic measurements manually and time used to perform the measurements automatically.

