## 7.2 Subject Procedure

### Part 1

The purpose of the procedure in the Part 1 is to calculate the accuracy of Ligence Heart manual functions that are used to perform echocardiographic measurements comparing it with the accuracy of manual measurements performed with other CE marked state-of-the-art medical image viewers. Measurements made in Ligence Heart software will be compared with CE marked software “IntelliSpace Cardiovascular 5.1” (Phillips) and “EchoPAC” version 112 from GE Healthcare.

One cardiologist will perform 2D TTE measurements of each patient on each system 2 times. Time difference between repeated measures must be at least two days.

### Part 2

The purpose of the procedure in the Part 2 is to compare Ligence Heart automatic measurements accuracy and reliability with human cardiologists in real clinical setting.

Four physicians will make 2D TTE measurements of each subject study 2 times. Physicians cannot share thoughts or results between themselves. Time difference between repeated measures must be at least two days. Measurements of three physicians will be used in modeling and results of the 4th will be used as a validation with automated system.

During both parts, time used for the analysis of the 2D TTE images will be recorded. During manual 2D TTE image analysis, time it takes for physician to make measurements will be registered. Stopwatch starts when physician opens study in Ligence Heart and stops when all listed measurements are made. In the use case including automatic measurements, the time it takes for automatic system to make measurements and physician to correct/validate the results is registered.

Summary of the clinical investigation parts

#	Analysis	Purpose	TTE Examination Protocol	Measurements
Part 1	Manual Measurement Analysis	To calculate the accuracy of Ligence Heart manual functions that are used to perform echocardiographic measurements comparing it with the accuracy of manual measurements performed with other CE marked state-of-the-art medical image viewers.	One physician will make 2D TTE measurements of each patient on each system 2 times. Time difference between repeated measures must be at least two days.	
 
• AoS (PLA)
 
• RVB (A4CH)
 
• LVEDV (A4CH)
 
• LVEDV (A2CH)
 
• RVEDA (A4CH)
 
• RAA (A4CH)
 
• AV-Vmax
 

UAB Ligence	Clinical Investigation Report	2021-04-09
		Rev: 1.0

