## 12 Statistical Methods

### 12.1 Statistical Hypotheses

UAB Ligence	Clinical Investigation Report	2021-04-09
		Rev: 1.0

The following hypotheses will be tested with the statistical methods:

1. The manual functionalities of Ligence Heart provide equally accurate tools for echocardiography evaluation compared to other state of the art CE marked medical software.
2. Automatic functionalities of Ligence Heart software perform echocardiography image analysis with non-inferior accuracy compared to a cardiologist.
3. Automatic functionalities of Ligence Heart software perform echocardiography image analysis with lower intra-rater variability compared to a cardiologist.
4. Automatic functionalities produce measurement values faster than a cardiologist.

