#### 12.4.2 Data analysis

Two-way ANOVA will be employed to test for significant differences between measurements made in different medical imaging software. Interrater reliability coefficient and Pearson correlation coefficient will be calculated to check the level of interchangeability between software.

Intrater reliability coefficient interpretation

Interpretation	Value
Slight	0.00-0.20
Fair	0.21-0.40
Moderate	0.41-0.60
Substantial	0.61-0.80
Almost perfect	0.81-1.00

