## 15.1 Manual functionalities (Part 1)

All measurements performed manually using Ligence Heart were equally accurate and reliable when compared to state-of-the-art certified medical image analysis software. Median inter-software reliability was 95.52% (IQR 94.31 - 97.17) with the lowest value observed for RAA (89.30%) and the highest for APV (99.26%). All tested measurements had inter-software reliability above 0.8, corresponding to high level of agreement between different platforms (**Table 2**) and there was no significant difference in the measurements produced by Ligence Heart in comparison to other CE marked state of the art medical device software.

**Table 2.** Inter-software reliability for Ligence Heart compared to EchoPAC and Intellispace Cardiovascular.

Measurement (abb.)	Measurement (full)	Inter-software reliability
AoS	Aortic sinus diameter	97.81%
RVB	Right ventricle basal diameter	93.28%
LVEDV4A	Left ventricle end diastolic volume (A4Ch)	97.12%
LVEDV2A	Left ventricle end diastolic volume (A2Ch)	93.95%
RVEDA	Right ventricle end diastolic area	92.17%
RAA	Right atrium area	89.30%
APV	Aortic peak velocity	99.26%
PTRV	Peak tricuspid regurgitation velocity	97.18%
E	Transmitral E velocity	99.21%
SP	S prime right ventricle lateral wall	97.16%
Dec	Transmitral E velocity deceleration time	95.41%
ACT	Acceleration time	95.52%
AVVTI	Aortic valve maximum velocity time integral	98.21%
TR VTI	Tricuspid regurgitation velocity time integral	94.66%
LVEDV	Left ventricle end diastolic volume (biplane)	95.52%

UAB Ligence	Clinical Investigation Report	2021-04-09
		Rev: 1.0

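### Part 1 concludes that the manual tools are equally reliable, but no planned statistic compares Ligence Heart's own repeat error with that of EchoPAC or IntelliSpace

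*Protocol*

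**What the plan says.** **Aim.** The manual-measurement objective (numbered 4 in Section 5.2.1) is "To calculate the reliability of Ligence Heart manual functions that are used to perform echocardiographic measurements", compared with other CE marked viewers. Section 4.2 goes further: "The manual functionalities of Ligence Heart are expected to provide equally accurate and reliable tools for echocardiography evaluation".

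**Hypothesis and endpoint.** Hypothesis 1 in Section 12.1 mentions accuracy only: "The manual functionalities of Ligence Heart provide equally accurate tools for echocardiography evaluation compared to other state of the art CE marked medical software". The matching endpoint in Section 5.3.1 is agreement between programs: "The inter-software reliability between manual measurements performed with Ligence Heart and other CE marked state-of-the-art medical image viewers will be calculated".

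**Design.** Section 7.2, Part 1: "One cardiologist will perform 2D TTE measurements of each patient on each system 2 times", and "Time difference between repeated measures must be at least two days".

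**Analysis.** Section 12.4.1 brings the repeats in through a single MSE on nt(m − 1) degrees of freedom, pooled over the programs. Section 12.4.2 plans three statistics: a test of software differences ("Two-way ANOVA will be employed to test for significant differences between measurements made in different medical imaging software"), one reliability coefficient, and a Pearson correlation. Section 12.3 confines all non-ANOVA calculations to the formulas in Section 12.

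**Conclusion.** Section 15.1 (Part 1): "All measurements performed manually using Ligence Heart were equally accurate and reliable when compared to state-of-the-art certified medical image analysis software". Table 2 supports this with one coefficient per measurement. Section 16.3 then states that every performance expectation of Section 4.2 was met. Run 1 against run 2 results appear only in Section 15.3, for the Part 2 cardiologists, and not by program.

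**The concern.** Agreement between programs and repeatability within a program are different properties. A viewer whose tracing or caliper tool gives more scattered repeat values is a less reliable tool even if its average is right. In Section 12.4 any extra scatter in Ligence Heart is averaged with the scatter of the two established programs before it enters the coefficient. A claim that Ligence Heart is as reliable as they are needs its repeat error set beside theirs, and neither the plan nor Table 2 does this. The reliability half of the Section 15.1 wording, carried into Section 16.3, therefore has no comparison behind it. The gap cannot be put down to an unseen analysis plan, because Section 12.3 closes the list of formulas and this same document reports the results.

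**Working it through.** **Inputs from the Protocol.** t = 3 programs, m = 2 readings (7.2); n = 58 analysed, 54 planned (15.1 Demographic data, 12.2); coefficient formula (12.4.1); median coefficient 0.9552, lowest 0.893 for RAA, 0.8 as the mark applied (15.1 Part 1).

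**Assumptions.** Ligence Heart repeat-SD ratio k = 2, no systematic software difference, no patient-by-software interaction. The documents give no repeat error by program.

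**1. The plan's own sample size.** For a within-between interaction, λ = f²·N·m/(1 − ρ) = 0.0625 × 54 × 2/0.4 = 16.9, on 2 and 51 df. The smallest N is 53, which rounds to 54 for three equal groups, with power 0.956. The stated 54 is reproduced, but it concerns an effect on means, not repeatability.

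**2. Effect of a doubled repeat SD on the coefficient.** Set the patient variance to 1. Under the assumptions, ρ = 1/(1 + mean error variance over the three programs).
- Equal programs at 0.9552: error variance = 0.0448/0.9552 = 0.0469.
- Doubling one SD: mean = 0.0469 × (4 + 1 + 1)/3 = 0.0938, so ρ = 1/1.0938 = 0.914.
- Ligence Heart alone: 1/(1 + 4 × 0.0469) = 0.842.
- From RAA's 0.893: error variance 0.1198, doubled to 0.2396, so ρ = 0.807.

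**3. Reading the reported values backwards.** A pooled 0.9552 also arises with comparator error variance 0.0469/2 = 0.0235. The comparators are then at 1/1.0235 = 0.977 and Ligence Heart at 1/(1 + 4 × 0.0235) = 0.914. Table 2 cannot tell this from three equal programs.

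**4. Simulation with the 12.4.1 formulas** (n = 58, k = 2):

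| Comparator coefficient | Pooled ρ above 0.8 |
|---|---|
| 0.955 | over 99.9% |
| 0.943 | over 99% |
| 0.92 | about 91% |
| 0.90 | 61% to 68% |
| 0.893 (RAA) | about half |

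The 0.90 range depends on whether negative variance-component estimates are set to zero. Fourteen of the 15 coefficients in Table 2 are at or above 0.92. At 0.955, a coefficient above 0.8 together with a non-significant ANOVA occurs in about 94% of trials, practically the same as for an equally repeatable tool.

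**5. The missing comparison, on the same readings.** Each program supplies n repeat pairs. Ligence Heart's repeat variance over the pooled variance of the two comparators is an F ratio on n and 2n df (58 and 116).
- Power at k = 1.5: 0.93 (n = 54) or 0.94 (n = 58). At k = 2: above 0.999.
- 95% CI for the SD ratio: about ×/÷ 1.25.
- If the true ratio is 1, the upper limit falls below 1.5 with probability 0.94 and below 1.25 with probability 0.48 (n = 58).
- For all 15 measurements at 1.5, assuming independence: 0.94¹⁵ ≈ 0.40.

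**The case against.** **Reliability has an operational meaning here.** Section 5.3.1 pairs the objective with inter-software reliability, and Section 12.4 computes that. This stands for the endpoint. It does not cover the broader statement about the tools in Sections 4.2 and 15.1.

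**The planned correlations carry information.** With three programs, a noisier one lowers both of its pairwise correlations and leaves the third unchanged. At 0.955 with a doubled SD, simulated correlations of two-reading averages were 0.944, 0.944 and 0.977, and the two Ligence Heart pairs were lowest in 99.9% of runs. This stands within that model. However, Section 12.4.2 does not say that the correlations are pairwise, sets no rule for comparing them, and Table 2 does not report them. Nor can correlations separate repeat error from patient-by-software interaction.

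**The purpose of the repeats.** A reader might infer that two readings were taken in order to compare repeatability. The documents do not say so. Their stated use is the pooled MSE, which separates error from interaction.

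**Passing.** A reader might infer that a tool with twice the repeat error simply passes. Section 12.4 fixes no pass mark, and at RAA's level the chance is about even.

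**The ANOVA.** Its non-significance in about 94% of simulated trials is close to its alpha level, because no shift was simulated. It is no evidence that real shifts would be missed.

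**Cause.** One cardiologist reads on all three systems, the comparators were already installed at the site, and Section 16.2 attributes variation partly to choice of video, cycle and frame. An unfavourable ratio need not be due to the software alone.

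**Conclusion.** The point holds in a limited form. Equal reliability of the manual tools is expected in Section 4.2 and concluded in Section 15.1, but the planned and reported Part 1 analysis contains no comparison of repeat error between programs. With a doubled Ligence Heart repeat SD the pooled coefficient falls only from 0.955 to about 0.91. It stays above 0.8 in nearly all trials at that level and in about half at 0.893. These figures rest on an assumed SD ratio and on no software bias or interaction.

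A reader might infer that Ligence Heart is in fact less repeatable. Nothing in the documents shows that: the reported values fit equal repeatability as well as a twofold difference. What is unsupported is the claim of equality. The inter-software agreement result is not affected by this point.

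**What to change.** In Section 12.4.2 add, for each of the 15 measurements, the repeatability SD of each program from its own two readings. Add the ratio of Ligence Heart to the comparators with a 95% CI, either by bootstrap over studies or from F on n and 2n df. State that the ratio may partly reflect the single reader's familiarity with each program and choice of frame.

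Let any statement of equal reliability rest on the interval against a bound with a stated justification. As results are already reported, a bound set now must be labelled post hoc. If no bound can be justified, give the ratios descriptively, limit the Section 15.1 conclusion to inter-software agreement, remove the reference to reliability, and align Section 16.3.

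The cost is a few lines of analysis and no new readings. The downside is that the claim may narrow for some measurements. Even a truly equal tool would meet a bound of 1.25 on any one measurement only about half the time, and a bound of 1.5 on all 15 in roughly 40% of studies if measurements were independent.
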